"Risk" is a broad term used to convey the potential for harm, burden, and inconvenience related to research participation. Use this section to provide a comprehensive description of foreseeable physical, psychological, social, interpersonal, and economic risks introduced by the research. Include the source of the information. Consider both the probability and magnitude of harm and its impact. Describe the foreseeable harms associated with the research (untoward effects of a medication) and those related to delay to individualized treatment. Include data from the literature, and local data, if available, on risk rates and subject experiences with research procedures. Describe

procedures in place to minimize risk. In general, please create a numbered list of risks/categories of risk, and in general put the list in the order of significance or level of risk, the most significant risks first followed by others.

1. Submaximal Cardiopulmonary Test Risks

There exists the possibility of certain changes occurring during the test. These include abnormal blood pressure; fainting; irregular, fast, or slow heart rhythm; and, in rare instances, heart attack, stroke, or death. Every effort will be made to minimize these risks by evaluation of preliminary information relating to the participant's health and fitness and by careful observation during testing. Emergency equipment and trained personnel are available to deal with unusual situations that may arise. Since this is a submaximal exercise test, the risks associated are those typical of any physical activity, and are low.

The submaximal cardiopulmonary exercise test will be conducted in the Behavioral Medicine laboratory on the 16th floor of the Presbyterian Hospital Building. It will be administered by [name], a Masters level exercise physiologist. According to the Handbook of Sports Medicine and the American College of Sports Medicine [6], participants at low risk can be supervised during this test by non-physicians without a physician being immediately available. [name] is certified at a level of basic life support (cardiopulmonary resuscitation [CPR]) and has automated external defibrillator (AED) training. The exercise testing facility also has a written medical emergency response plan with procedures and contact numbers and is equipped with an AED.

2. Training Program Risks

The risks associated with exercise training are those typical of any physical activity. All participants will have been carefully screened prior to the initiation of the exercise protocol to minimize the risk of adverse events.

Participants will be required to present a note from a physician indicating medical clearance for exercise training.

3. Blood Draw Risks

Blood samples will be drawn by trained phlebotomists.

During the blood draw, the participant may feel slight pain from the needle or experience some dizziness. She may also develop a temporary bruise where the needle was inserted.

4. Peanut Consumption Risks

Although we are currently unaware of any risks, there may be possible risks to the dietary intervention, such as previously unknown allergies.

Subjects will be screened for known peanut allergies and monitored for signs of allergic reactions.

Methods to Protect Confidentiality

Describe the data management plan and the methods you will employ to protect subject privacy and the confidentiality of research data. The section should detail how information will be collected, recorded, coded, stored, transmitted, and as applicable, shared with other investigators so as to minimize risks related to breach of confidentiality. Confirm that

identifiers are removed, to the extent possible, from research data, and explain if there are links between subject identity and research data, or if the data is anonymous. Also, indicate where the data is stored, who is responsible for its safekeeping, and who has access to subject identity and codes, if any, which cross-link research data and subject identity. Confirm that identifiable data is not collected, stored, or transmitted by mail, fax, on removable drives, laptops, or via the internet without proper protections, e.g. encryption.

There are two areas in which safeguards to protect participants from undue risk require discussion: procedures used to obtain informed consent and those used to insure confidentiality of participants' responses and findings on tests. In the consent form and in discussion with an investigator, participants will be advised fully of the procedures to be used, the amount of time required of them, the possible risks and benefits of the procedures, their right to refuse participation in the study without prejudice, their right to terminate participation at any moment without prejudice, and the name and telephone number of the Principal Investigator. In the informed consent form, participants are told that the information they provide and all findings will be kept strictly confidential, with access limited to the research staff and the possible exception of state or federal regulatory personnel. No one but designated project staff will have access to the master list linking participants' names to subject identification numbers, and all information obtained will be coded. Data will be analyzed without reference to personal identifying information, and this information will be carefully protected within the database. All paper files will be kept in locked file cabinets.

Direct Benefits to Subjects

Describe only benefits to individual subjects that are likely to accrue during the study itself. Do not include subject compensation or treatment to be provided at the end of the study, as these do not figure into the IRB's risk benefit considerations. Do not describe diagnostic and evaluation components unless subjects receive clinical feedback. Do not describe the anticipated scientific benefits of the research. Some studies offer no direct benefit to subjects.

The cardiorespiratory benefits of moderate exercise are well known. Additionally, evidence suggests that peanut consumption is also cardioprotective; a substantial body of evidence exists that demonstrates the beneficial impact of nut consumption on cardiovascular disease outcomes and all-cause mortality. Any information that is important to the participant's health will, with the participant's written permission, be transmitted to their physician.

References

1. Ridker, P.M. and T.F. Luscher, *Anti-inflammatory therapies for cardiovascular disease*. Eur Heart J, 2014. **35**(27): p. 1782-91.

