7. Medications that alter inflammation or autonomic nervous system activity.	
8. Any history of psychosis or ECT	

9. Psychotic disorder (lifetime)			
10. Current or recent (past 5 years) Major Depressive Disorder, Bipolar Disorder, or Anxiety disorder			
11. Current or recent (within past 12 months) alcohol or substance abuse or dependence. Recent use (past month) of recreational drugs.	Medical History Interview		
12. Probiotic and dietary supplements that affect inflammation or the ANS			
13. Physically active	CPET1	VO _{2max} (ml/kg/min)	VO _{2max} (ml/kg/min)
	Age (yrs)	Male	Female
	21-29	>41.0	>35.2
	30-39	>39.5	>33.8
	40-49	>37.6	>32.3
14. Peanut allergy in subject or in family of subject. Subjects who are unsure of their allergy status will be excluded.	Diet Interview		
15. Hormonal Birth Control	Telephone Screen		

Study Procedures

Provide a clear, concise narrative of study procedures with special attention to the subjects' involvement. Detail the overall study timeline and location of study procedures, list all interventions, assessments and interviews, estimate the duration of each procedure, provide dosing schedules, identify study personnel involved in each procedure, and provide credentials for relevant personnel. For complicated study designs, we strongly encourage attaching tables, flow-charts, and study algorithms.

Sedentary, overweight or obese but otherwise healthy 21-45 year old participants from Columbia University Medical Center/New York Presbyterian Hospital, and surrounding community, will be recruited through posted flyers **and the Columbia RecruitMe online platform**. After screening and eligibility determination through physical activity assessment and medical history interview they will provide informed consent. Participants must agree to maintain constant body weight(<±3%) and current levels of physical activity, except for the study interventions, throughout the protocol. They must also agree to abstain from omega-3 fatty acids supplements, high fat fish consumption (>8oz/week), and nuts (besides the peanuts given). Additionally, high quantities (>1 serving/day) of flax seeds, chia seeds, soy, canola, including oils, or food products that contain these ingredients in high quantities must be avoided, but subjects can otherwise maintain their current diet. The experimental protocol is presented in the Flowchart.

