Qualifying participants will undergo a two-week run-in period, first of control snack consumption and then stretching to screen for adherence. They will then undergo a submaximal cardiopulmonary exercise test, sCPET 1, to establish baseline $VO_{2\max}$ and confirm eligibility as a sedentary individual. They will then proceed to Lab Session 1.

Women will be asked to wait until they are in the post-ovulatory mid-luteal phase of their menstrual cycle (as indicated by a home ovulation kit) to schedule the first sCPET, such that all their later sCPET and laboratory tests will similarly align with the mid-luteal phase.

Women participants receive a 7-day ovulation home kit at the start of the study to estimate the ovulation date. The kit contains strips on which participants are asked to urinate every day following the end of their menstrual period until ovulation is detected – measured by a surge in luteinizing hormone (LH), also known as the onset of the luteal phase. All study tests are scheduled for this period within the menstrual cycle.

Participants will then be randomized to either 4 weeks of high intensity interval aerobic exercise or peanut consumption (2 times a day). Participants starting with peanuts will meet with the research assistant/dietitian who will assess their eating patterns by implementing a 24 hour recall. Dietary information will be used to help guide the subjects in maintaining an isocaloric diet during the protocol. Additionally, the Mifflin St. Jeor calculation will be used to determine the daily number of calories needed for each subject in order to maintain their weight.

All adherent and qualifying subjects go on to Laboratory Session 1 (anthropomorphic indices, HRV, fasting blood drawn). Participants starting with the exercise intervention will be instructed on how to use the exercise facility, and participants starting with peanuts will be given peanuts and instructed on food substitution in order to maintain an isocaloric diet. All contact with participants about group assignment, test scheduling, adherence monitoring, etc. is conducted by trained research assistant “coaches.”

After the first 4-week intervention (exercise or peanuts) all participants will undergo Laboratory Session 2 and sCPET 2, and proceed to a 4-week washout period.

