By the end of the washout period, all participants will undergo sCPET 3. Participants who cross-over to the dietary peanut intervention will meet with the research assistant/dietitian to assess their eating patterns to inform instructions on maintaining an isocaloric diet during the protocol. Participants who cross-over to the exercise intervention will be instructed on how to use the exercise facility. All participants will return for Laboratory Session, and participants who will be consuming peanuts will be given peanuts and instructed on food substitution in order to maintain an isocaloric diet.

Following the second 4-week intervention, all participants return for follow-up Laboratory Session 4 and sCPET 4. All outcome variables (VO_{2max}, HRV, inflammation, and PBMC's) and control variables (weight, body composition and diet quality and physical activity independent of training) will be collected at 4 time periods in the study. All contact with participants about group assignment, test scheduling, adherence monitoring, etc. is conducted by trained research assistant “coaches.”

Two-Week Run-in Period

In previous projects, the run-in period has allowed us to identify participants likely to adhere to the protocol and thus has substantially reduced dropout.

For the first week, participants will eat a run-in snack, commercially available pita chips, twice a day as between meal snacks. Research assistants will collect the numbered pita packets at the end of the week to check for compliance. Only participants who consume at least 11 out of the 14 pita snacks and maintain weight will continue to the second week of the run-in.

For the next week, participants will be instructed on how to perform the stretching phase of the run-in and how to use the Polar Heart Rate (HR) monitor. Participants will complete 4X/week for 30 min of stretching at home while wearing the Polar HR monitor. Coaches will provide detailed instructions on how to complete the stretching.

Stretches consist of arm circles, neck rotations, toe reach, gluteal stretches, lateral leg swings, achilles stretch and ankle rolls. Adherence will be monitored using gym attendance records and HR monitor data. Only participants who perform at least 3 out of the 4 stretching sessions can continue on to the sCPET, Lab Session 1, and randomization.

Submaximal Cardiopulmonary Exercise Test

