We will administer a sub-maximal test using a pre-recorded audiotape with instructions and timed metronome rhythms and a 12" step (see figure). The participant will listen to the test instructions and will commence stepping to the metronome beat at 15 steps per minute for a 2-minute period following which heart rate, measured by telemetry (Model RS400, Polar Electro OY, Finland) and rating of perceived exertion on the Borg Scale

(see figure) will be recorded (Test Level 1). The step rate then will be increased to 20 steps per minute for an additional 2 minutes, when heart rate and rating of perceived exertion will again be recorded (Test Level 2). The test will continue with additional 2 min increments increasing the step rate by 5 steps/min until the participant reaches a heart rate of 80% of the predicted maximal heart rate equation (220-age) or estimates perceived exertion at a score of 17 or greater. The maximum test duration will be 10 minutes (i.e., Test Level 5). Each individual's aerobic capacity then will be predicted by plotting the exercise heart rates on a prepared graphical datasheet, drawing a visual line of best fit between the data points, projecting the line up to maximum heart rate (HR) and estimating the corresponding aerobic capacity (ml O₂/kg/min) from the x-axis. This estimate of aerobic capacity will be used to establish target heart rate for the 4-week training period.

6	No exertion
7	
8	
9	
10	
11	Light
12	
13	Somewhat hard
14	
15	Hard (heavy)
16	
17	Very hard
18	
19	
20	Maximal exertion

Additionally, as illustrated in inclusion criteria chart, the sCPET1 will be used to determine sedentary status which is a requirement for subjects.

Dietary Assessment

Participants who have successfully completed the run-in, the sCPET1, who have been randomized, and who are beginning the peanut intervention will meet with a research assistant who will assess their eating patterns using a 24 hour recall (USDA Multiple-Pass Method [52]). This will inform recommendations for a stable, isocaloric eating pattern. Subjects must refrain from consuming foods or supplements listed in exclusion criteria. Caloric needs are calculated using the Mifflin-St Jeor prediction equation [53].

Participants must abstain from omega-3 fatty acids supplements and high fat fish consumption (8oz/week), nuts, flax seeds and chia seeds, soy (including soybean oil and canola oil) and food products that contain these ingredients in high

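### Minor: VO2max at sCPET 1–4, which also decides exclusion 13, is read from a line drawn by eye; a fixed least-squares calculation on the same heart rates would make it repeatable at little cost

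*Protocol*

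**What the plan says.** The step test raises the rate every two minutes "until the participant reaches a heart rate of 80% of the predicted maximal heart rate equation (220-age") or until perceived exertion reaches 17 or more. "The maximum test duration will be 10 minutes (i.e., Test Level 5"), so there are at most five heart rates to plot. Aerobic capacity is then found by "drawing a visual line of best fit between the data points, projecting the line up to maximum heart rate (HR") and reading the matching x-axis value on a prepared datasheet.

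The result has three uses:

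- **Eligibility.** In the Inclusion/Exclusion Criteria, "13. Physically active" is ascertained by the first test against VO2max cut-offs by age and sex, from 32.3 to 41.0 ml/kg/min. The test section says that "the sCPET1 will be used to determine sedentary status which is a requirement for subjects", and Study Procedures says the test is done to establish baseline VO2max "and confirm eligibility as a sedentary individual".
- **Outcome.** Study Procedures lists VO2max first among the outcome variables, which "will be collected at 4 time periods in the study".
- **Training.** The test section says the same estimate is used to establish the target heart rate.

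No calculated fit, repeat reading or masked reading is described.

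**The concern.** A line drawn by eye through three to five points has no unique position, and here it must be extended well beyond the data. If the test stops exactly at 80% of 220 − age, the remaining distance is 0.2 × 199 = 39.8 bpm at age 21 and 0.2 × 175 = 35.0 bpm at age 45. A small difference in tilt is magnified over that distance.

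Two things are at stake. Close to a cut-off, a person could be admitted or excluded according to how the line was drawn rather than what was recorded. And each of the four outcome readings carries noise that a calculation on the same data would not have.

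**Working it through.** There is no figure in the plan to reproduce: it gives no reading error, and the datasheet is not shown. The check asks how far a plausible drawing error moves the reading for someone whose VO2max lies at a cut-off.

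**Inputs from the Protocol.** Maximum heart rate is 220 − age; the test has at most five levels; the exclusion 13 cut-offs at ages 30–39 are 39.5 (men) and 33.8 (women).

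**Assumed inputs.** Age 33, so maximum heart rate is 187. Level 1 has a heart rate of 105 and costs 15 ml/kg/min. Four levels are completed. Heart rate rises r = 15–18 bpm per level and oxygen cost rises c = 3–5 ml/kg/min per level. The drawn line misses the least-squares position at the first and last levels by independent errors of SD s = 1–2 bpm.

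**Formula.** Let t = (187 − 105) / (3r), the projection as a multiple of the plotted range. To first order,

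SD of reading = s × (c/r) × √[(1 − t)² + t²].

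- r = 15: t = 82/45 = 1.82, square root = 2.00.
- r = 18: t = 82/54 = 1.52, square root = 1.60.

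**Restricting to people at a cut-off.** VO2max = 15 + 82 × c/r. Hence c/r = 18.8/82 = 0.229 at 33.8, and 24.5/82 = 0.299 at 39.5.

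| Cut-off | r (bpm) | c (ml/kg/min) | SD, s = 1 | SD, s = 2 |
|---|---|---|---|---|
| 33.8 | 18 | 4.13 | 0.37 | 0.74 |
| 33.8 | 15 | 3.44 | 0.46 | 0.92 |
| 39.5 | 15 | 4.48 | 0.60 | 1.19 |

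At 39.5 with r = 18, c would be 5.38, outside the assumed range. Simulation with 400,000 draws per case gives almost the same values (0.37 to 1.21). Letting every input combination run free gives a wider span, 0.27–1.35 for four levels. But with level 1 at 15 ml/kg/min, those extremes belong to VO2max values of about 29 and 42, not to people at these two cut-offs.

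**Meaning near a cut-off.** The chance that the by-eye reading falls on the other side from the least-squares reading is Φ(−d/SD), with d the distance from the cut-off. For d = 0.5 it runs from Φ(−0.5/0.37) = 9% to Φ(−0.5/1.19) = 34%. For d = 1.0 it runs from under 1% to 20%. These are disagreements with least squares, not with true fitness.

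**Meaning for the outcome.** For mean change in the 20 completers, the added standard-error component is SD × √(2/20): 0.12 to 0.38 ml/kg/min. For scale, the 9% gain cited in the HIIT section is 0.09 × 32.3 = 2.9 to 0.09 × 41.0 = 3.7.

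**Compared with 220 − age.** A 10 bpm error in maximum heart rate moves the reading by 10 × c/r = 2.3 to 3.0. Taken as one SD, it is raised by the by-eye step by a factor of √[1 + (s × root/10)²], that is by 1% (s = 1, root 1.60) to 8% (s = 2, root 2.00).

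**Second model.** A separate calculation used 4–5 ml/kg/min per level, a heart rate of 65 at 3.5 ml/kg/min, and a line tilted in opposite directions at its two ends. A tilt of 1 bpm moved the reading by about 0.4–0.9 ml/kg/min, and 2 bpm by about 0.8–1.9. The order of size is the same.

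**The case against.** The strongest reply is that the procedure is complete and standardized as written (timed audio, fixed step, prepared datasheet), so the change is a preference with no bearing on the aims. Much of this stands. VO2max is in none of the three hypotheses, this is a pilot, and the larger errors, extrapolation and 220 − age, are untouched. With an assumed 3 bpm residual SD, the error left after least squares is about 0.9–1.8 ml/kg/min, comparable with or above the noise removed. With exactly two plotted points the line is already determined, and only plotting and reading error is saved.

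There are also partial safeguards. The Baecke questionnaire makes the initial assessment of sedentary status, although its threshold is stated differently in the consent section and the inclusion table, a separate matter. One exercise physiologist is named to administer the test, so the issue is mainly one reader's consistency.

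What does not fall away is that the Protocol itself fixes a reading rule with no unique answer and applies it to cut-offs given to one decimal. Error in 220 − age should also largely repeat across one person's visits, whereas drawing error is fresh each time and so counts for more in within-person change.

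A reader might infer three stronger points that the documents do not support:

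- **That the peanut–exercise comparison is compromised.** sCPET 1 precedes randomization, so its reading affects who enters, and the cytokine comparison does not use VO2max.
- **That the reader knows the assignment and leans accordingly.** Masking is not stated, but neither is unmasking. The Protocol says "All contact with participants about group assignment, test scheduling, adherence monitoring, etc. is conducted by trained research assistant" coaches.
- **That least squares brings VO2max closer to true fitness.** It makes the reading repeatable and little more.

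**Conclusion.** The point holds as a minor, cheap improvement. The Protocol fixes a by-eye reading for a quantity that decides an exclusion and is a listed outcome, and a calculation on the same data would remove the variation from line drawing. Its size is roughly 0.4–1.2 ml/kg/min (SD) per reading for someone near a cut-off. That figure is illustrative: oxygen cost, heart-rate rise, number of levels and placement error are all assumed. It would matter for candidates within about 1 ml/kg/min of a cut-off and adds modest noise to a listed outcome. It does not touch the stated hypotheses.

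**What to change.** 1. At every sCPET, replace the visual line with ordinary least squares of all recorded level heart rates on the datasheet's own oxygen-cost values, solved at 220 − age, in one fixed script applied identically at sCPET 1–4. This single value is the VO2max for exclusion 13 and for the outcome.
2. Keep the plot, if at all, as an unscored check for keying errors, with no numeric trigger; correct documented entry errors only. A trigger of, say, 2 ml/kg/min would fire in about 14% of error-free readings if the by-eye SD were 1.35.
3. If fewer than two levels are completed, or the fitted line does not rise, record VO2max as not obtained. The sponsor should state in advance how exclusion 13 is then ascertained.
4. Because the Protocol uses the same estimate to establish target heart rate, the sponsor should state which value feeds that step, so that two VO2max values do not coexist. No change to the training rule is proposed.

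The cost is a few sentences and one formula, with no new visit or data. The x-axis values must be transcribed and checked once. With so few points, the first and last heart rates carry most of the leverage.

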Our aims are to test the hypotheses that:

1. Plasma levels of IL-6 and TNF- α are reduced by peanut consumption and that this effect is at least as great as the effect of high-intensity aerobic exercise.
2. Consistent with the cholinergic anti-inflammatory hypothesis, peanut consumption and high intensity exercise will be associated with an increase in heart rate variability.
3. Mitochondrial enzymatic activity is altered in response to both interventions: exercise and peanut consumption

Inclusion/Exclusion Criteria

This section details your study sample(s) and addresses the requirement for risk minimization.

You may choose to divide your sample by population (healthy controls vs. subjects) or by procedure (subjects who will have an MRI) and then define different sets of criteria for each.

For each sample, create or insert a table to describe detailed criteria for study inclusion and exclusion and the method you will use to ascertain each criterion. The method of ascertainment may describe tests, scales and instruments. When relevant, indicate the level of training of the person who will make the assessment (e.g. clinical interview by a psychiatrist).

Inclusion/Exclusion Criteria needs to be numbered and listed in outline form (see Table template below).

INCLUSION CRITERIA	METHOD OF ASCERTAINMENT
Of either sex, age 21–45 years English-speaker	Telephone screen
Overweight or obese	BMI 27.0 – 34.9 kg/m ²
Sedentary	Baecke Physical Activity Questionnaire of <10
Home computer access	Participant disclosure

[figure not shown]
EXCLUSION CRITERIA	METHOD OF ASCERTAINMENT
1. Cardiovascular disease	Medical History Interview
2. Uncontrolled high blood pressure (blood pressure \geq 140/90). Individuals with controlled hypertension (i.e. under medical treatment) and blood pressure lower than 140/90 will not be excluded.	Measurement taken at consent before eligibility is determined
3. Current or recent (evidence of disease x 5 years) non-skin neoplastic disease or melanoma. Prostatic carcinoma will not be grounds for exclusion.	
4. Active hepatic disease (not a history of hepatitis) or primary renal disease requiring dialysis, primary untreated endocrine diseases, e.g., Cushing's disease or primary hypothalamic failure or insulin dependent diabetes (Type I or II).	Medical History Interview
5. HIV infection	
6. Pregnant or lactating (participation allowed 3 months after ceasing lactation).	

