quantities (>1 serving/day) during the study but can otherwise maintain their current diet. Participants are assessed for alcohol, caffeine, and cocoa consumption and must maintain their levels of intake of throughout the study.

Laboratory Testing Sessions

Participants abstain from any physical exercise for a 24-hour period prior to each testing session to control for acute effects of exercise on inflammatory markers. Participants arrive for Laboratory Sessions in the morning after an overnight fast. 45 ml (9 teaspoons) of venous blood will be drawn for cytokine, PBMCs and hormone analysis. For women, laboratory sessions are scheduled in the mid-luteal phase of the menstrual cycle, to control for cycle effects on Heart Rate Variability [54]. After the blood draw, they receive a light breakfast providing 15% daily energy intake as established during the dietary assessment. Waist circumference is measured with a Gulick anthropometric tape. Height is measured using the Seca 214 Portable Height Rod (Seca Corp., Hamburg, Germany). Weight and body composition are measured using a Tanita BF-350 monitor (Tanita UK Ltd., Middlesex, UK).

Participants then are instrumented with ECG leads and respiration monitoring bands and rest quietly in the supine position for 5 min, after which 20 min of resting ECG and respiration data are collected. These data are collected in all Laboratory Sessions.

Treatment Conditions

In this crossover design, participants are randomly assigned to either the peanut condition followed by aerobic exercise or aerobic exercise followed by the peanut condition. Following the guidelines for non-inferiority trials, the exercise intervention, as the more widely accepted anti-inflammatory treatment, functions as the comparison for the peanut intervention.

Peanut Diet

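### Resting HRV, the Aim 2 outcome, is recorded after an in-session breakfast with no fixed meal-to-ECG interval; recording it before the meal is a cheap improvement

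*Protocol*

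**What the plan says.** The order of a session is set in the Protocol, Study Procedures, Laboratory Testing Sessions. "Participants arrive for Laboratory Sessions in the morning after an overnight fast". A 45 ml blood sample follows. "After the blood draw, they receive a light breakfast providing 15% daily energy intake", sized from the dietary assessment. The text next lists waist, height, weight and body composition with their instruments, and continues: "Participants then are instrumented with ECG leads and respiration monitoring bands and rest quietly in the supine position for 5 min". After that rest, 20 minutes of ECG and respiration are recorded. "These data are collected in all Laboratory Sessions".

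No time between breakfast and ECG is stated, and no reason is given for placing the meal first. The summary of Laboratory Session 1 earlier in Study Procedures describes only the blood as fasting. Nothing elsewhere puts the ECG before the meal.

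HRV is the outcome of the second aim in Specific Aims and Hypotheses, which expects that "peanut consumption and high intensity exercise will be associated with an increase in heart rate variability". Body composition has a lesser role, as one of the "control variables (weight, body composition and diet quality and physical activity independent of training) will be collected at 4 time periods".

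**The concern.** Participants are already fasted when they arrive, so a fasting HRV recording is available at each session, yet the written order gives it up. If HRV depends on recent eating and on the time since eating, each HRV value carries a component set by how long the meal, the measurements and the electrode placement happened to take that day. The same section fixes menstrual phase because of its effect on HRV, so the plan accepts that this outcome needs controlled conditions. Meal timing is left open.

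Two things are at stake. The first is precision: timing noise enters each HRV value and so each within-period change, in a study that needs only 20 completers. The second is possible bias: if four weeks of training or of peanuts changes the HRV response to a meal, a recording made after the meal mixes that change with any change in resting HRV.

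**Working it through.** **Order of steps.** Arrival fasted, blood draw, breakfast, ECG set-up, 5 min rest, 20 min recording. The word *then* makes the order explicit for the ECG. For waist, weight and body composition it is only implied by the order of the sentences.

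**Meal size.** The Peanut Diet section equates 400 to 600 kcal with 20% of daily energy.
- Daily energy: 400 / 0.20 = 2000 kcal; 600 / 0.20 = 3000 kcal.
- Breakfast at 15%: 0.15 × 2000 = 300 kcal; 0.15 × 3000 = 450 kcal.

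**Timing.** Assume 10 to 15 min for body measurements and electrode placement (not in the Protocol). Adding 5 min of rest, recording starts 15 to 20 min after the meal and ends 20 min later, at 35 to 40 min.

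**Effect on precision.** The Protocol gives no alpha, power, HRV standard deviation, target effect or size of meal effect, so there is no planned figure to reproduce. What follows is an illustration.
- n = 20 completers (Description of Subject Population).
- Assumed: two-sided alpha 0.05, 80% power, paired comparison, normal approximation.
- f = extra within-person error variance from meal timing, as a share of the remaining error variance (assumed 0.10, 0.25, 0.50).
- The SD is that of the within-person difference without this noise.

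Minimum detectable effect (MDE) = (1.960 + 0.842) / √n × √(1 + f).

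With f = 0: 2.802 / √20 = 0.63 SD.

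Equivalent completers = 20 / (1 + f). Power at the effect that had 80% = Φ(2.802 / √(1 + f) − 1.960).

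| f | MDE (SD) | Equivalent completers | Power |
|---|---|---|---|
| 0 | 0.63 | 20 | 80% |
| 0.10 | 0.66 | 18.2 | 76% |
| 0.25 | 0.70 | 16.0 | 71% |
| 0.50 | 0.77 | 13.3 | 63% |

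Recording before the meal returns this component to f = 0.

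**The case against.** The strongest reply is that the meal is a set share of energy, given at every session, and that each participant is compared with himself or herself. An average meal effect therefore largely cancels. That stands, and it rules out a general claim that HRV is biased. What is left is timing noise and a possible change in the meal response under an intervention.

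The reply can go further. The Protocol gives no size for a meal effect on HRV, and the same steps are repeated each time; the timing assumption above spans only 5 minutes. This also stands in part. The table shows what given amounts of noise would do, not that they occur. It does not remove the point, because no interval is set and nothing in the text keeps it constant.

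Some stronger readings are tempting but not supported:

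- A reader might infer that the recording measures the autonomic response to a meal. It does not: without a recording before the meal there is no response to compute, only a level after eating.
- A reader might take it as fact that weight and bioimpedance follow the meal. The text says "Weight and body composition are measured using a Tanita BF-350 monitor" with no sequencing word, so this is an inference.
- A reader might object that fasting cytokines are being explained by fed HRV. Aim 2 as written concerns only an increase in HRV; no mediation analysis is stated.
- A reader might infer that breakfast size is unset for those who start with exercise, because the dietary assessment is described for those beginning peanuts. Other sentences speak of estimating energy needs for each subject, so the text does not settle this.

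**Conclusion.** The point holds as a cheap improvement. As written, HRV is recorded after a breakfast of about 300 to 450 kcal at all four sessions, with no fixed interval, although participants arrive fasted. The likely harm is avoidable within-person noise in the Aim 2 outcome. Bias is possible only if an intervention changes the response to the meal.

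The size is not known. That eating and the time since eating affect resting HRV is itself an assumption here, since the Protocol does not address it. If the added error variance were 10% to 50%, the MDE with 20 completers would be 0.66 to 0.77 SD in place of 0.63 SD, under the assumed alpha and power. This is a pilot and HRV belongs to its second aim, so the point does not undermine the study. It remains worth acting on because later analysis cannot recover a fasting recording that was never made.

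**What to change.** In Laboratory Testing Sessions, put the steps in this order: fasting blood draw; weight, waist and bioimpedance; 5 min supine rest; 20 min ECG and respiration recording; breakfast. State explicitly that weight and bioimpedance are taken before breakfast, since their order is now only implied. Keep the same order at all four sessions of any one participant, because a change part-way would itself shift the within-person differences.

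The cost is small but not zero. Breakfast is delayed by the 25 min of rest and recording plus the body measurements and set-up. At the 10 to 15 min assumed above, that is 35 to 40 min, and roughly 30 to 45 min allowing for variation, after a 45 ml draw. No visit, procedure or staff is added.
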